8.5.1 Analysis of secondary endpoints

(1) Mean Hb values at Weeks 48 and 52 of the treatment period

Descriptive statistics for change from Hb on the first day of the treatment period to mean Hb at Week 48 and Week 52 in the treatment period should be calculated by treatment group. The MMRM is used to model the mean Hb values at each evaluation time point based on the following model, and the mean Hb values at Week 48 and Week 52 of the treatment period for each treatment group should be obtained, and the least squares mean (LSMean), its standard error, and 2-sided 95% CIs for the mean Hb values should be calculated, and the point estimate of the between-group difference (MT-6548 -

darbepoetin) of LSMean, its standard error, and 2-sided 95% CI should be calculated. No analysis will be performed for patient cohorts.

[MMRM Model]

- Covariate: response variable value of the first day of the treatment period
- Fixed effects: Treatment group, evaluation time point, patient cohort (Correction or Conversion cohort), interactions of evaluation time point \times treatment group, interactions of patient cohort (Correction or Conversion cohort) in evaluation time point
- Degrees of freedom adjustment: Kenward–Roger method
- Covariance matrix within subject for each subject: unstructured (type = UN; unstructured)
When it was not converged using unstructured as a covariance matrix within subject variance, the setting of the covariance matrix within subject variance will be changed in the following order, and the analysis will be carried out using the covariance matrix within subject variance converged first.
Heterogeneous Toeplitz (TOEPH) \rightarrow Heterogeneous AR (1) (ARH [1]) \rightarrow Heterogeneous CS (CSH) \rightarrow Toeplitz (TOEP) \rightarrow First-order autoregressive (AR [1]) \rightarrow Compound symmetry (CS)
- Random effects: subjects

(2) Hb values at each evaluation time point in the treatment period

1) Hb values at each evaluation time point in the treatment period

Hb value and change of Hb values from the first day of the treatment period at each evaluation time point of the treatment period will be obtained, and its descriptive statistics should be calculated for each treatment group. Before and after comparison will be conducted for changes of Hb from the first day of the treatment period to each evaluation time using the paired t-test. In the Conversion and Conversion ($Hb \geq 11.0$ g/dL) cohorts, no test will be conducted for the difference between the baseline value and each evaluation time point during the treatment period in the darbepoetin alfa group.

A group comparison should be conducted using an MMRM (with compound symmetry [CS] for a covariance matrix within subject variance) similar to the analysis of “(1) Mean Hb values at Week 48 and Week 52 of treatment”. LSMean, its standard errors, and 2-sided 95% CI will be calculated for Hb value at each evaluation time point of the treatment period, and the point estimate, its standard errors, 2-sided 95% CI, and p-value will be calculated for the group difference (MT-6548 – darbepoetin) of the LSMean by treatment group.

A group comparison should be conducted for the change from the first day of the treatment period using the MMRM (with compound symmetry [CS] for a covariance matrix within subject variance). LSMean, its standard errors, and 2-sided 95% CI should be calculated for change at each evaluation

time point from the first day of the treatment period, and point estimate, its standard errors, 2-sided 95% CI, and p-value should be calculated for the group difference (MT-6548 – darbepoetin).

The time course diagram will be prepared for mean Hb values in each evaluation time point in the treatment period by treatment group. 95% CI of the mean will be represented by an error bar.

In the Conversion and Conversion ($Hb \geq 11.0$ g/dL) cohorts, no test will be conducted for the group difference.

2) Analysis of timing of administration of MT-6548 tablets (before meal, after meal, other)

An analysis similar to “1) Treatment period Hb at each evaluation time point in the treatment period” should be conducted by the timing of administration of MT-6548 tablets (before meal, after meal, other). However, this analysis is only for the MT-6548 group; neither tabulation in the darbepoetin group nor comparison with the darbepoetin group is performed. No analysis will be performed for patient cohorts.

3) Analysis by previous ESA formulation type

An analysis similar to “1) Treatment period Hb at each evaluation time point in the treatment period” should be conducted by the type of previous ESA formulation (epoetin alfa or epoetin beta, darbepoetin alfa, epoetin beta pegol). Only Conversion, Conversion ($Hb \geq 11.0$ g/dL), and Conversion ($Hb < 11.0$ g/dL) cohorts should be analyzed, and the data should be summarized in the MT-6548 group only.

4) Analysis by dose of previous ESA formulation types

An analysis similar to “1) Treatment period Hb at each evaluation time point in the treatment period” should be conducted for weekly dose of previous ESA formulation (darbepoetin alfa, epoetin beta pegol: ≥ 15 µg, < 15 µg; 2 categories) by type of previous ESA formulation (darbepoetin alfa, epoetin beta pegol). The number of patients classified by dose was set to be almost equal.

Only Conversion, Conversion ($Hb \geq 11.0$ g/dL), and Conversion ($Hb < 11.0$ g/dL) cohorts should be analyzed, and the data should be summarized in the MT-6548 group only.

5) Analysis of Hb value on the first day of the treatment period

An analysis similar to “1) Treatment period Hb at each evaluation time point in the treatment period” should be conducted for the Hb value on the first day of the treatment period (divided the number of subject into 3 categories at tertiles). The Conversion ($Hb < 11.0$ g/dL) cohort should be summarized in the MT-6548 group only. Time course diagram for mean and 95% CI should be prepared separately by treatment group. No statistical test will be conducted for the group difference and the difference between baseline and each evaluation time point in the treatment period for the darbepoetin alfa group in the Conversion cohort and Conversion ($Hb \geq 11.0$ g/dL) cohort.

6) Analysis with or without iron supplements and iron-containing phosphate binders

An analysis similar to “1) Treatment period Hb at each evaluation time point in the treatment period (LSMean, standard error, and two-sided 95% CIs will not be calculated for changes from the start of

the treatment period.)" should be conducted for subjects continuously using iron supplements or iron-containing phosphate binders and subjects never using iron supplements and iron-containing phosphate binders during the treatment period. Analysis should be performed only in the MT-6548 group, and no analysis using the MMRM model will be conducted for patient cohorts. However, subjects who uses intravenous iron at least once should be excluded from the tabulation.

Since intravenous iron should be included in the tabulation for treatment period phase 1, the tabulation for treatment period phase 1 should be output again.

7) Analysis by iron supplements and iron-containing phosphate binders formulations

An analysis similar to "1) Treatment period Hb at each evaluation time point in the treatment period" except for the analysis using the MMRM should be conducted for subjects continuously using iron supplements or iron-containing phosphate binders during the treatment period. Analysis should be performed only in the MT-6548 group, and no analysis will be performed for patient cohorts. However, subjects who uses intravenous iron at least once should be excluded from the tabulation.

8) Analysis of Hb value at Week 52 and CRP values on the first day of the treatment period

For MT-6548 group only, a scatter plot chart should be provided after linear regression with the following variables. No analysis will be performed for patient cohorts.

x: Logarithmic CRP value on the first day of the treatment period

y: Hb values at Week 52 of the treatment period

(3) Proportion of subjects whose Hb level during the treatment period is within the target range (11.0 g/dL to <13.0 g/dL) or outside the target range (<10.0 g/dL or ≥ 13.0 g/dL)

The number, proportion, and 95% CI (Clopper-Pearson [Exact] method) of subjects with Hb value within the target range (11.0 g/dL to <13.0 g/dL, within), <11.0 g/dL (below), and ≥ 13.0 g/dL (above) at each time point of the treatment period should be provided by treatment group. McNemar tests should be used for before and after comparison (ratio of subjects within the target range and out of target range) on the first day and each evaluation time point of the treatment period.

Point estimate, its 95% CI (exact method), and p-value (Fisher's exact test) of subject proportions should be calculated for the between-group difference (MT-6548 – darbepoetin) of Hb values in each category (within the target range [11.0 g/dL to <13.0 g/dL], <11.0 g/dL or ≥ 13.0 g/dL) at each evaluation time point of the treatment period.

The proportion of subjects in each Hb category (within the target range [11.0 g/dL to <13.0 g/dL], <11.0 g/dL or ≥ 13.0 g/dL) at each evaluation time point of the treatment period should be provided as a stacked bar graph assuming that the number subjects of each treatment group at the evaluation time point is 100%. Stacked bar charts should be generated separately for each treatment group. No statistical test will be conducted for the group difference and the difference between baseline and each

evaluation time point in the treatment period for the darbepoetin alfa group in the Conversion cohort and Conversion (Hb ≥ 11.0 g/dL) cohort.

(4) Number of days from the first day of the treatment period required to reach the target Hb range (≥ 11.0 g/dL to < 13.0 g/dL)

Descriptive statistics should be calculated for number of days required from the first day to reach target Hb range (11.0 g/dL to < 13.0 g/dL) of the treatment period. The number of days should be calculated as the first evaluation day when the target Hb range (11.0 g/dL to < 13.0 g/dL) is reached minus first day of the treatment period plus 1. If target Hb range (11.0 g/dL to < 13.0 g/dL) is not reached, it should be calculated as the final day of evaluations minus first day of the treatment period plus 1.

Kaplan-Meier plots for the number of days required from the first day to reach target Hb range (11.0 g/dL to < 13.0 g/dL) of the treatment period should be provided for each treatment group.

No subjects with an Hb value of ≥ 11.0 g/dL on the first day of the treatment period will be included in the tabulation.

Only the Correction and Conversion (Hb < 11.0 g/dL) cohorts should be analyzed. The Conversion (Hb < 11.0 g/dL) cohort should be summarized in the MT-6548 group only.

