Descriptive statistics will be calculated for days from the first day of the treatment period required to reach target Hb range (11.0–13.0 g/dL). A Kaplan-Meier plot will be shown for days from the first day of the treatment period required to reach target Hb range (11.0–13.0 g/dL). Statistical summaries will not include subjects with Hb of ≥ 11.0 g/dL on the first day of the treatment period.
- 5) Correction cohort only: Rate of increase of Hb levels

Descriptive statistics will be calculated for rate of Hb increase and treatment groups compared with ANCOVA using baseline values as covariates. Point estimates and their standard errors and their 95% CI will be calculated for differences in mean values between the MT-6548 group and the darbepoetin group.

(3) Other endpoints

Incidence and ratios will be shown for discrete data, while descriptive statistics will be calculated by treatment group for continuous data.

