13.4 Changes in statistical analysis protocol

If any portion of the statistical analysis plan is modified prior to data lock, reasons for change will be described in the statistical analysis protocol and the clinical study report. If the analysis plan is modified or analyses added after data lock, reasons for modification will be described in the statistical analysis protocol and the clinical study report, and analytical results will be distinguished from the original plan.

14. Study protocol compliance, deviation, and modification

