8.1.2 Descriptive statistics to calculate

Types of continuous variables to be calculated for each descriptive statistics item are provided below. Number of subjects, mean, standard deviation (SD), median, minimum, maximum, and 2-sided 95% CI of the mean

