8.2.2 Subjects who discontinued or interrupted their treatment

For subjects enrolled in the treatment period, the number and proportion of discontinued subjects should be calculated in each treatment group and by reasons for discontinuation. Subjects who entered specific comments ("Criterion for liver function") according to the input rules should be counted for the number of subjects discontinued by reasons that meet the discontinuation criteria for abnormal hepatic function values.

Items: Number and proportion of discontinued subjects by treatment group and the number and proportion of reasons for discontinuation for subjects enrolled in treatment period,

In addition, for subjects enrolled in the treatment period, the number and proportion of discontinued subjects should be calculated in each treatment group and in every 12 weeks (unit: from first day of the treatment period [Day 1] to Day 84, Days 85–168, Days 169–252, and after Day 253.

Items: Number and proportion of subjects discontinued in each treatment group in subjects enrolled in the treatment period

For subjects enrolled in treatment period, the number cases of drug interruption should be tabulated by treatment group and the number and proportion of cases by reasons for interruption should be tabulated. The denominator of the proportion should be the sum of the number of interruption cases. If there are multiple reasons for a single interruption, they should be counted for each reason and stated as the number of interruption cases. For drug interruption due to abnormal hepatic function, subjects who entered specific comments according to the input rules ("Criterion for liver function") should be calculated.

Items: Number of drug interruptions in subjects enrolled in the treatment period and number and ratio of drug interruptions by reasons for drug interruption

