8.7.4 Individual adverse events

(1) Summary of adverse events and adverse drug reactions

The number (number of subjects with adverse events) and proportion of subjects in whom the following adverse events are observed at least once after the administration of the study drug to the end of the follow-up period should be calculated for each treatment group. Unless otherwise specified, no analysis will be performed for patient cohorts.

- Adverse event
- Adverse drug reaction
- Serious adverse event
- Serious adverse drug reaction
- Adverse event leading to discontinuation
- Adverse events leading to dose reduction or interruption of the study drug (active drug)
- Adverse events resulting in death (adverse event leading to death)

(2) Individual adverse events

If a difference from treatment period 1 occurs in “(1) Summary of adverse events and adverse reactions”, the number of subjects and the incidence rate of individual adverse events classified by SOC and PT in MedDRA Version 20.1 and MedDRA/J Version 20.1. (hereinafter the same) should be calculated.

The SOC will be sorted by order of international consensus, the PT by descending order of the number of subjects with MT-6548 and by descending order of the number of subjects with darbepoetin (PT code ascending when the number is equal). Unless otherwise specified, no analysis will be performed for patient cohorts.

(3) Fundoscopy

The frequency of each decision result (normal, clinically nonsignificant abnormal, or clinically significant abnormal [Presence or absence of retinal hemorrhage, presence or absence of retinal oedema]) should be calculated at each evaluation time point, and a shift table composed of the decision results (normal, clinically nonsignificant abnormal, or clinically significant abnormal) should be provided on the first day of the treatment period and each evaluation time point.

9. Software to Use

SAS for Windows (Release 9.4) will be used for statistical analysis.

10. Changes in the Statistical Analysis Plan from the Study Protocol

No change from the study protocol.

11. References

Errata

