The proportion of subjects in each Hb category (within the target range [11.0 g/dL to < 13.0 g/dL], < 11.0 g/dL or ≥ 13.0 g/dL) at each evaluation time point of the treatment period should be provided as a stacked bar graph assuming that the number subjects of each treatment group at the evaluation time point is 100%. Stacked bar charts should be generated separately for each treatment group. The Conversion (Hb value < 11.0 g/dL) cohort should be analyzed only in the MT-6548 cohort. No statistical test will be conducted for the group difference and the difference between baseline and each evaluation time point in the treatment period for the darbepoetin alfa group in the Conversion cohort and Conversion (Hb value ≥ 11.0 g/dL) cohort.

(3) Number of days from the first day of the treatment period required to reach the target Hb range (≥ 11.0 g/dL to < 13.0 g/dL)

Descriptive statistics should be calculated for number of days required from the first day to reach target Hb range (11.0 g/dL to < 13.0 g/dL) of the treatment period. The number of days should be calculated as the first evaluation date reached target Hb range (11.0 g/dL to < 13.0 g/dL) – first date of the treatment period + 1. If target Hb range (11.0 g/dL to < 13.0 g/dL) is not reached, the final date of evaluations – first date of the treatment period + 1 should be assumed.

Confidential

Kaplan-Meier plots for the number of days required from the first day to reach target Hb range (11.0 g/dL to <13.0 g/dL) of the treatment period should be provided by treatment group.

No subjects with an Hb value of ≥ 11.0 g/dL on the first day of the treatment period will be included in the calculation.

Only the Correction and Conversion (Hb value < 11.0 g/dL) cohorts will be analyzed. The Conversion (Hb value < 11.0 g/dL) cohort will be tabulated in the MT-6548 group only.

(4) Hb increase rate

Descriptive statistics should be calculated for the Hb increase rate (g/dL/week) by treatment group. Between-group comparisons by analysis of covariance (ANCOVA) should be performed using Hb on the first day of the treatment period as a covariate. LSMean, its standard errors, and 2-sided 95% CI of Hb increase rate (g/dL/week) should be calculated by treatment group. The point estimate of the between-group difference (MT-6548 – darbepoetin) of LSMean, its standard errors, 2-sided 95% CI, and p-value should be calculated.

The Hb increase rate should be analyzed by 2 methods defined in the “4.10 Hb increase rate”.

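### The days-to-target table counts the last evaluation day of a subject who never reached target as a time to target, so its mean and interval depend on how long failures were followed

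*SAP*

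**What the plan says.** Both SAPs build one variable, the number of days. A subject who reaches the range gets the first in-range evaluation day, minus the first treatment day, plus 1. For a subject who does not, Final SAP 8.5.1 (4) says that the value "is not reached, it should be calculated as the final day of evaluations minus first day of the treatment period plus 1". In Phase 1 SAP 8.5.2 (3), "the final date of evaluations – first date of the treatment period + 1 should be assumed".

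Descriptive statistics are then calculated on this variable. Section 8.1.2 of each SAP defines them: "Number of subjects, mean, standard deviation (SD), median, minimum, maximum, and 2-sided 95% CI of the mean". The only exclusion based on Hb is a first-day value of 11.0 g/dL or more, so subjects who never reach the range stay in. Kaplan-Meier plots of the same days are also planned, without a statement of which subjects are censored. Only the Correction and Conversion (Hb <11.0 g/dL) cohorts are analysed, and the latter in the MT-6548 group only.

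Protocol 13.3.2 is shorter: "Descriptive statistics will be calculated for days from the first day of the treatment period required to reach target Hb range", together with a Kaplan-Meier plot. It gives no rule for subjects who never reach the range.

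**The concern.** For someone who never reaches the range, the last evaluation day says only that the time to target is longer than that. A Kaplan-Meier estimate uses this information correctly. A mean, an SD and a t-type interval do not, because they treat it as an observed time.

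The direction of the distortion depends on when failures stop being observed, and the plan ties that to failing. Under Protocol 8.5.3 and 12.1, rescue before the Week 24 tests means withdrawal, and an investigator may withdraw a subject whose Hb cannot be brought into range. Section 7.3 of each SAP drops efficacy data from the day after rescue. An early failure is thus entered as a short time to target and a late failure as a very long one. A reader of the table cannot tell slow response from no response, and an arm with more early failures could look faster.

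**Working it through.** **The plan's own figure.** The documents give none for this endpoint. Their only design figure is a probability above 95% with 150 per arm, SD 1.78 g/dL and margin -0.75 g/dL. It reproduces (95.4%) and is not affected by this point.

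**Inputs from the documents.** Protocol Table 9.1-1 counts the start as Day 0, Week 24 as Day 168 and Week 52 as Day 364. A subject followed to schedule without reaching target therefore gets 168 + 1 = 169 in the Phase 1 table and 364 + 1 = 365 in the final table. The Correction cohort target is 100 at 1:1, so at most about 50 per arm.

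**Step 1: one arm, same responses, different last day.** Mean = (sum of reach days + k × L)/n, with k subjects not reaching and last day L. Assumed: n = 50, k = 10, and 40 reach days (4, 7, 7, 6, 5, 5, 4 and 2 subjects at days 15, 29, 43, 57, 71, 85, 113 and 141). The reach days sum to 2,420, a mean of 60.5.

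| L | Mean | SD | 95% CI | Median | Max | Kaplan-Meier median |
|---|---|---|---|---|---|---|
| 15 | (2,420 + 150)/50 = 51.4 | 35.4 | 41.3 to 61.5 | 43 | 141 | 57 |
| 57 | (2,420 + 570)/50 = 59.8 | 30.3 | 51.2 to 68.4 | 57 | 141 | 71 |
| 169 | (2,420 + 1,690)/50 = 82.2 | 53.3 | 67.1 to 97.3 | 71 | 169 | 71 |
| 365 | (2,420 + 3,650)/50 = 121.4 | 126.7 | 85.4 to 157.4 | 71 | 365 | 71 |

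Early exit pulls the mean below that of the subjects who did reach target (60.5). The ordinary median moves only when failures leave early, or if about half or more never reach target.

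**Step 2: between the two locks.** Each subject followed to schedule without reaching target adds (365 − 169)/50 = 3.92 days to the mean of an arm of 50. Five, ten or fifteen such subjects add 19.6, 39.2 or 58.8 days.

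**Step 3: can the arms be mis-ordered?** All rates here are assumptions. Time to target is exponential with median 70 days, observed at the scheduled visits. A share f can never reach target: 5% in one arm, 30% in the other. By Day 364 the actual non-reaching shares are 8% and 32%. Subjects able to reach target have a tabulated mean of 109.26 days in the final table, so the arm mean is (1 − f) × 109.26 + f × E, where E is the mean exit day of those unable to reach it. The last column comes from 40,000 simulated trials with 50 per arm.

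| Exit of those unable to reach | E | Mean, 5% arm | Mean, 30% arm | Worse arm has shorter mean |
|---|---|---|---|---|
| Days 14–56 | 36 | 105.6 | 87.3 | 85% |
| Days 70–112 | 89.7 | 108.3 | 103.4 | 61% |
| All followed to Week 52 | 365 | 122.0 | 186.0 | 0.5% |
| Equal mix of the three | 163.6 | 112.0 | 125.6 | 26% |

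For 5% against 15% the last column is 66%, 54%, 13% and 39%. In the Phase 1 table, with follow-up ending at Week 24, 5% against 30% gives 88%, 50%, 5% and 43%.

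**The case against.** The strongest reply is that the failures are visible elsewhere. The Kaplan-Meier plot in the same paragraph is sound if non-reaching subjects are censored. Final SAP 8.5.1 (3) plans numbers and proportions below, within and above range that "at each time point of the treatment period should be provided by treatment group". Rescue rates are planned, and in Final SAP 8.2.2 "the number and proportion of discontinued subjects should be calculated in each treatment group and in every 12 weeks". This stands as a limit on the harm. However, none of these outputs, as described in the method text, gives the number who ever reached target. That text asks for Kaplan-Meier plots and no median. The lists of output tables and figures were not available, so it cannot be said that no such count or median exists.

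Three further objections hold. The rise from 169 to 365 reflects two locks with different horizons; it is not an error within either table, and a restricted mean would also rise with its horizon. The reversal rates rest on assumed failure shares and exit times, and exit by Day 56 for everyone is extreme. Criteria-based ESA rescue needs at least 2 weeks at maximum dose; on the stated dose steps and intervals, with a first increase at Week 2, that comes no earlier than about Day 56 for MT-6548 and Day 70 for darbepoetin. Discretionary rescue, transfusion and other withdrawals can come sooner. Lastly, Protocol 13.2 leaves further data-handling rules to the SAPs, so a reader should not infer that the last-day rule is an unrecorded protocol departure.

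**Conclusion.** The concern holds for the descriptive table. Both SAPs state a rule under which lower bounds are averaged with observed times, so the mean, SD, maximum and interval do not describe time to target unless everyone is followed to the same day. The shift with last day in Step 1 is arithmetic, but its size depends on the assumed number of failures and reach times.

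A reader might go further and infer that the table will favour the worse arm. The documents do not support that, because they give no exit timing. With full follow-up the mean behaves like a restricted mean and orders the arms correctly. Nor does the point touch the Kaplan-Meier plot, provided that the last day is treated as censored.

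The scope is narrow. Phase 1 SAP 8.5.4.7 treats secondary endpoints as exploratory, no between-group test is planned here, and the arms can be compared only in the Correction cohort, with at most about 50 each. The non-inferiority analysis and sample size are unaffected. It should be corrected because the repair is nearly free.

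**What to change.** In both SAPs:

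1. State that the last evaluable day of a subject who has not reached target is a censoring time.
2. Replace the pooled descriptive statistics with the number and percent reaching target and the Kaplan-Meier median with 95% CI, by arm. Note that censoring at rescue or withdrawal may be informative. The two belong together: in the 30% arm of Step 3 the Kaplan-Meier median is 85, 113, 141 or 113 across the four exit patterns, although half of all subjects have reached target by Day 141 in each.
3. Preferably add the cumulative proportion reaching target, with rescue or withdrawal counted as not reaching.
4. Do not compare arms on a table limited to subjects who reached target. It conditions on success, and in the Step 3 model the worse arm looks faster in about 50% of trials under every exit pattern. If such a table is kept, label it as conditional and show it beside the percent reaching.

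Because the protocol asks for descriptive statistics, record the replacement. Protocol 13.4 requires that for a change before data lock "reasons for change will be described in the statistical analysis protocol and the clinical study report"; for a change after lock, it also asks that the results be distinguished from the original plan. Final SAP section 10 and Phase 1 SAP section 9, which now read "No change from the study protocol", would each need an entry.

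The cost is one revised table and one entry per SAP, with no new data. The summary may look slightly less favourable, and the intervals will be wide at this cohort size.
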